7.6.2. Addressing Missing Data for the Secondary and Exploratory Efficacy

Missing individual item scores of the full BPI-DPN will be imputed for the calculation of the average score within a domain using the average score across the non-missing items within the domain at a subject's visit provided that the proportion of missing items scores within that domain is less than 25%; otherwise, the domain score at that visit is missing.

The same method as the full BPI-DPN will be used when addressing the missing data for SF-36 and EQ-5D.

Individual item scores on the MNSI (both physical assessment and history) questionnaire will not be imputed. The total MNSI scores will be imputed using a "worst-case" imputation approach. Missing individual items will be imputed as the category corresponding to the largest number of points in the total score calculation. This equates to a response of "Yes" to questions 1-3, 5-6, 8-9, 11-12, and 14-15 and "No" to questions 7 and 13 on the history assessment. On the physical assessment, it equates to a response of "No" on the "Appearance of Feet" question, a response of "Present" on the "Ulceration" question, and a response of "Absent" on the "Ankle Reflexes", "Vibration perception at great toe", and "Monofilament" questions.

Missing PGIC and BST scores and the use of rescue medication will not be imputed.

Missing values from the cytokine profiles and anti-hepatocyte growth factor (HGF) antibody results will not be imputed as they are a part of the safety assessment.

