### **8.3.2.3. EuroQol Health Utilities Index**

The EuroQol Health Utilities Index (EQ-5D) instrument (Section 10.10, Appendix 10) will also be administered through use of an eDiary. The Investigator should ensure that the Participant is provided with instructions and is trained to use the eDiary and to complete the assessment tool properly before data collection begins to measure the Participant's perception of their overall health status pre-dose on Days 0 and 90 and on Day 180/ET. The instrument has two parts – the descriptive system that measures mobility, self-care, usual activities, pain/discomfort, and anxiety/depression; and the visual analog scale that records the Participant's self-rated health.

Upon completion of the questionnaire, the study coordinator will check the questionnaire for completeness. Any omissions or ambiguous answers will be clarified by the Participant prior to leaving the clinic.

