4. STUDY ENDPOINTS

4.1. Primary Efficacy Endpoint

- Proportion of Responders (≥ 20, 30, 40, 60 and 70% reduction in the means of the ADPSs from the BPI-DPN) from the 7 days prior to the Day 0 Visit to the 7 days prior to the Day 90 Visit and the 7 days prior to the Day 180 Visit for Engensis compared to Placebo
- Changes in the means of the Average Daily Pain Scores (ADPSs) from the BPI-DPN from the 7 days prior to the Day 0 Visit to the 7 days prior to the Day 90 Visit for Engensis compared to Placebo
 - This will be calculated the same way described in Section 4.1.
- Changes in the severity scores (Average Pain, Worst Pain, Least Pain and Pain Right Now)
 from the full BPI-DPN from the 7 days prior to the Day 0 Visit to the 7 days prior to the Day
 90 Visit and to the 7 days prior to the Day 180 Visit for Engensis compared to Placebo
 - The severity score consists of four scores (Average Pain, Worst Pain, Least Pain and Pain Right Now), and the overall average of the scores can be calculated. The change in each score will be calculated and analyzed separately.
- Changes in Michigan Neuropathy Screening Instrument (MNSI) from Baseline to Day 90 and to Day 180 for Engensis compared to Placebo
 - The MNSI comprises a Participant questionnaire (15 questions) with two domains: Physical Assessment and History. The change will be calculated for each domain separately.
- Changes in Quality of Life in the 36-item Short Form Health Survey (SF-36) from Baseline to Day 90 and to Day 180 for Engensis compared to Placebo
 - The SF-36 survey has 8 domains and 2 component scores; the 8 domains include Physical Functioning, Social Functioning, Role—Physical, Role—Emotional, Bodily Pain, General Health, Vitality, and Mental Health, and the 2 component scores include a Physical Component score and Mental Component score. The change will be calculated for each domain and component score separately.
- Changes in Quality of Life in the EuroQol Health Utilities Index (EQ-5D) from Baseline to Day 90 and Day 180 for Engensis compared to Placebo
 - EQ-5D has 2 main parts. Part 1 is the descriptive system and Part 2 is the visual analog scale of self-rated health. Part 1 consists of 5 questions assessing: Mobility, Self-Care, Usual Activities, Anxiety/Depression and Pain/Discomfort. The overall health state value index combining the 5 questions of Part 1 in EQ-5D will be calculated. The overall scores and change in each Part will be calculated and summarized.

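### The SAP's average-the-other-items rule for missing answers does not suit EQ-5D Part 1 and should not be extended to it (minor, exploratory endpoint)

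*SAP*

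**What the plan says.** SAP Section 7.6.2 gives the rule for the full BPI-DPN. A missing item is filled, so that a domain average can be formed, by "using the average score across the non-missing items within the domain" at that visit. The condition is "provided that the proportion of missing items scores within that domain is less than 25" per cent; at or above that limit the domain score is missing. The next sentence carries the rule over: "The same method as the full BPI-DPN will be used when addressing the missing data for SF-36 and EQ-5D". No exception or adaptation for EQ-5D follows.

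The exploratory endpoint list in SAP Section 4 (printed under the 4.1 heading in the supplied copy) describes the instrument. "Part 1 consists of 5 questions assessing: Mobility, Self-Care, Usual Activities, Anxiety/Depression and Pain/Discomfort". The output is a single value, not an average: "The overall health state value index combining the 5 questions of Part 1 in EQ-5D will be calculated". Part 2 is the visual analogue scale. Scores and change are planned for each Part.

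Protocol Section 8.3.2.3 has the coordinator check the EQ-5D for completeness at the visit: "Any omissions or ambiguous answers will be clarified by the Participant prior to leaving the clinic".

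**The concern.** Filling an item with the mean of its neighbours assumes that the items are repeated measures of one thing and that the score is their average. Neither is true of EQ-5D Part 1. Its five answers are separate category levels that together define a health state, and the index is attached to that state. Mobility, self-care, usual activities and mood may correlate with pain, but their mean is not an answer to the pain question.

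Two things are at stake. The programmer may be handed a value that is not a level, with no instruction on what to do next. Or an index may enter the Day 90 or Day 180 analysis that depends on a level the participant never gave.

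**Working it through.** The plan states no figure to reproduce here. The check applies its threshold to its own item counts.

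**Inputs**
- Condition for filling: m/k < 0.25, where m of k items in a domain are missing (SAP 7.6.2).
- Fill value: mean of the k − m answered items (SAP 7.6.2).
- EQ-5D Part 1: k = 5 (SAP Section 4).
- Number of response levels per EQ-5D question: not shown in the documents, so 3 and 5 are both assumed.

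**Step 1: does the rule act on EQ-5D?**

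| Reading of a domain | k | m | m/k | Filled? |
|---|---|---|---|---|
| Part 1 as one domain | 5 | 1 | 20% | Yes |
| Part 1 as one domain | 5 | 2 | 40% | No |
| Each dimension its own domain | 1 | 1 | 100% | No |
| Visual analogue scale | 1 | 1 | 100% | No |

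On the first reading the rule acts when exactly one answer is missing. On the second it never acts and the sentence is empty for EQ-5D.

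**Step 2: is the fill value a response level?** Take mobility 2, self-care 1, usual activities 2, anxiety/depression 1, with pain/discomfort missing. The fill is (2 + 1 + 2 + 1)/4 = 6/4 = 1.5, which is not a level.

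Listing every possible set of four answers:
- 3 levels: 3⁴ = 81 sets, of which 60 have a non-integer mean; 60/81 = 74.1%.
- 5 levels: 5⁴ = 625 sets, of which 468 have a non-integer mean; 468/625 = 74.9%.

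These shares count each set once. They show that a fractional fill is not a rare corner case; they do not predict how often it would occur in this trial.

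**Step 3: does the SAP resolve a fractional fill?** Section 7.6.1 rounds imputed pain scores to one decimal. Section 7.6.2 gives no rounding step, and one decimal would still leave 1.5. When the mean happens to be whole, the index can be computed, but it rests on a level taken from other dimensions.

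**Step 4: would a different threshold help?** With m/k ≤ 0.25, one missing EQ-5D answer (20%) is still filled and two (40%) are still not. The cut-off is not the problem; applying the method to this instrument is.

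**Side check, BPI-DPN severity.** With k = 4, one missing item is 1/4 = 25%, which is not less than 25%, so the four-item average is missing whenever any one item is missing.

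**The case against.** The strongest reply is that the SAP never defines a domain for EQ-5D, and that its rule serves a domain average, which EQ-5D does not have. On that view the rule may simply not apply. This stands as a point about wording, but it does not rescue the sentence, which is then either unsuitable or without function.

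Second, the public copy lists SAP Section 8.4.6 on exploratory endpoints in its contents, but the body of 8.4 is not in the supplied text. Derivation detail may be there. That limits what can be said about the analysis; it does not change what 7.6.2 instructs.

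Third, the practical effect is close to nil: the questionnaire is checked on the day, EQ-5D is exploratory, and SAP 7.4 treats exploratory p-values as supportive only. This stands and sets the size of the point.

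Three stronger readings are tempting, and the documents do not support them:
- *The rule makes pain look milder.* Participants enter with a pain score of at least 4, so one might expect a fill from the other dimensions to be too low. The documents give no EQ-5D data to show this. The rule is the same in both arms, and a filled pain answer is not itself a listed endpoint.
- *The BPI-DPN rule is defective because it cannot act on severity.* It covers the full BPI-DPN, which has content beyond the four severity items, such as question 9a. For severity the consequence is defined (score missing), the overall average is optional, and for the four scores the SAP says "The change in each score will be calculated and analyzed separately". That is a choice, not an error.
- *The SF-36 carry-over is equally wrong.* Nothing in the documents shows a defect there.

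**Conclusion.** The extension of the rule to EQ-5D is unsuitable as written. With Part 1 taken as one domain, which is the natural reading because it is the only multi-question unit and feeds one index, a single missing answer is filled with a value that does not measure the missing dimension and is often not a level. With one-item domains, the instruction does nothing.

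The size is minor. It touches only EQ-5D index values at visits with exactly one of five answers missing. The documents give no rate, and the check at the visit should keep it low. The primary pain endpoint has its own missing-data rule in SAP 7.6.1 and is unaffected. The conclusion does not depend on the number of EQ-5D response levels; only the 74.1% and 74.9% shares do.

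**What to change.** In SAP 7.6.2, remove EQ-5D from the carry-over sentence and add that:
- no EQ-5D item is imputed;
- the index is missing at a visit if any of the five Part 1 answers is missing;
- the visual analogue scale is summarised as observed.

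Check the wording against SAP 8.4.6 so that the two agree.

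The cost is a few sentences and minor programming, and a few index values that become missing rather than being filled. Protocol Section 9.3 allows the SAP to be finalised up to database lock, so this fits before then.

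Separately, and not as a correction, the sponsor should confirm that the optional four-item BPI-DPN severity average is meant to be missing whenever one item is missing, since that is what a strict limit below 25% produces.

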**MICHIGAN NEUROPATHY SCREENING INSTRUMENT**

## How to Use the Michigan Neuropathy Screening Instrument

**History.** The history questionnaire is self-administered by the Participant. Responses are added to obtain the total score. Responses of “yes” to items 1-3, 5-6, 8-9, 11-12, 14-15 are each counted as one point. A “no” response on items 7 and 13 counts as 1 point. Item #4 is a measure of impaired circulation and item #10 is a measure of general aesthenia and are not included in scoring. To decrease the potential for bias, all scoring information has been eliminated from the Participant version.

Upon completion of the questionnaire, the study coordinator will check the questionnaire for completeness. Note, the Participant will be asked to initial and date the questionnaire.

**Physical Assessment.** For all assessments, the foot should be warm ( $> 30^{\circ}\text{C}$ ).

[figure not shown]
**Foot Inspection:** The feet are inspected for evidence of excessively dry skin, callous formation, fissures, frank ulceration or deformities. Deformities include flat feet, hammer toes, overlapping toes, hallux valgus, joint subluxation, prominent metatarsal heads, medial convexity (Charcot foot) and amputation.

**Vibration Sensation:** Vibration sensation should be performed with the great toe unsupported. Vibration sensation will be tested bilaterally using a 128 Hz tuning fork placed over the dorsum of the great toe on the boney prominence of the distal interphalangeal (DIP) joint. Participants, whose eyes are closed, will be asked to indicate when they can no longer sense the vibration from the vibrating tuning fork. In general, the examiner should be able to feel vibration from the hand-held tuning fork for 5 seconds longer on his distal forefinger than a normal Participant can at the great toe (e.g., examiner’s DIP joint of the first finger versus Participant’s toe). If the examiner feels vibration for 10 or more seconds on his or her finger, then vibration is considered decreased. A study should be given when the tuning fork is not vibrating to be certain that the Participant is responding to vibration and not pressure or some other clue. Vibration is scored as 1) present if the examiner senses the vibration on his or her finger for  $< 10$  seconds, 2) reduced if sensed for  $\geq 10$  or 3) absent (no vibration detection.)

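### The worst-case rule for missing MNSI items has no cap and no visit restriction, so it can distort change from baseline in an exploratory endpoint

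*SAP*

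**What the plan says.** SAP 7.6.2 covers missing data for the secondary and exploratory efficacy scales. For the full BPI-DPN, a missing item takes the mean of the answered items in its domain, "provided that the proportion of missing items scores within that domain is less than 25%; otherwise, the domain score at that visit is missing". The SF-36 and EQ-5D follow the same method.

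The MNSI is treated differently. The paragraph opens with "Individual item scores on the MNSI (both physical assessment and history) questionnaire will not be imputed", continues with "The total MNSI scores will be imputed using a 'worst-case' imputation approach", and then gives the working rule: "Missing individual items will be imputed as the category corresponding to the largest number of points in the total score calculation". It spells this out for the history part as "a response of 'Yes' to questions 1-3, 5-6, 8-9, 11-12, and 14-15 and 'No' to questions 7 and 13 on the history assessment", and for the physical part includes "a response of 'Absent' on the 'Ankle Reflexes', 'Vibration perception at great toe', and 'Monofilament' questions". It gives no maximum number or share of missing items, names no visit, and does not mention a form that is missing altogether.

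SAP section 4 analyses MNSI as change from baseline to Day 90 and to Day 180, with the physical and history domains taken separately. The baseline MNSI is done at Screening (Protocol 1.3, SoA footnote 32).

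**The concern.** Worst-case imputation is usually defended as conservative. That holds for a value at follow-up. It does not hold for both ends of a change score. A high imputed value at follow-up looks like worsening, while a high imputed value at baseline looks like improvement once the item is answered later. One unrestricted rule cannot be conservative at both visits.

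The missing cap matters as well. With no limit, a form with a handful of answers still yields a total, and most of that total comes from the rule rather than from the participant. The more the arms differ in missed assessments, the more the MNSI contrast reflects missingness rather than neuropathy. MNSI change is one of the measures meant to show whether the drug improves neurological function, so its reading should not depend on who left items blank.

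The wording is also unsettled. The paragraph first says items are not imputed and then imputes them, so two programmers could produce different totals from the same data.

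**Working it through.** The plan states no figure for the effect of this rule, so there is none to reproduce. The check applies the rule literally.

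**Inputs**
- Scored history items (SAP 7.6.2): 11 items that score on a yes, plus items 7 and 13 that score on a no. Maximum = 11 + 2 = 13. Protocol Appendix 12 agrees, since "Item #4 is a measure of impaired circulation and item #10 is a measure of general aesthenia and are not included in scoring".
- Physical signs (SAP 7.6.2): five. Points per sign are not visible in this copy. Assumption: 1 point per sign per foot, maximum 10 (5 if only one foot is scored).
- Mean history score, missing rates and the probability *p* that a true answer scores: not in the documents, so assumed and shown as ranges.

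**Step 1: items missing at baseline.** Let *k* history items be missing at baseline, then be answered at follow-up with no true change. Expected spurious change = −*k*(1 − *p*).
- *k* = 1: −0.25 at *p* = 0.75, and −1 at *p* = 0.
- *k* = 3: −0.75 at *p* = 0.75, and −3 at *p* = 0.
- Any *k* at *p* = 1: zero.
- If the same item is missing at both visits, both get the same value and the spurious change is zero.

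**Step 2: effect of Step 1 on the arm comparison.** Assume 5% of baseline history items are missing and *p* = 0.5. Each arm shifts by −13 × 0.05 × 0.5 ≈ −0.32 points. A simulation with 76 per arm (the target of 152 split 1:1) gave a mean between-arm shift of 0.00, with a standard deviation of 0.09. Baseline gaps arise before randomization, so they cancel on average and leave only extra variability.

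**Step 3: follow-up.** If *u* history items are blank, the rule alone contributes *u* points, so a largely blank form scores near 13. If a wholly missing form is imputed as well, the spurious change is 13 − *b* for baseline score *b*:
- *b* = 4: +9
- *b* = 6: +7
- *b* = 8: +5

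Under the assumed 10-point physical form, *b* = 2.5 gives +7.5 and *b* = 6 gives +4.

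**Step 4: effect of Step 3 on the arm comparison.** With the same mean jump in both arms, bias = (difference in the proportion of blank forms) × (13 − *b*). For an imbalance of 5 percentage points:
- 0.05 × 9 = 0.45
- 0.05 × 7 = 0.35
- 0.05 × 5 = 0.25

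Equal proportions and equal jumps give zero.

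**Step 5: what the section's own limit would allow.** 3/13 = 23.1% is under 25%, and 4/13 = 30.8% is not, so at most 3 scored history items could be imputed. On the assumed 10-point physical form, 2/10 = 20% passes and 3/10 = 30% does not. A wholly missing form would stay missing.

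**The case against.** The case for leaving the rule alone has several parts.

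- **The text is silent on visits and on blank forms.** A reader might infer that the SAP prescribes worst-case scoring at baseline and a maximum score for every absent Day 180 form. It states neither. Its subject is missing items, which most naturally means a partly completed form. This stands, and the wholly missing case is only a plausible reading. It is plausible because SAP 7.6 lists early withdrawal and missed visits among its causes of missing data, because the rule is worded for total scores, and because 7.6.2 says outright when a scale (PGIC, BST) is not imputed. The mean-of-the-other-group method in SAP 7.6.1 also covers Day 0, so imputing at baseline is not foreign to the plan.
- **Baseline gaps do not favour either arm.** This stands (Step 2).
- **The trial has safeguards.** The coordinator checks the questionnaire for completeness (Protocol 8.3.4). The Screening physical score must reach 2.5 for entry (Protocol 5.1). The MNSI is on the early-termination list, if it can be done (Protocol 7.2). These make the problem rarer, above all for baseline physical items. They do not cover a missed visit, and the eligibility score does not protect the history domain.
- **The apparent contradiction has a coherent reading.** Item data stay as observed, and worst-case values serve only to build the total. That is probably the intent, so the sentence needs rewording rather than deletion.
- **The 25% limit belongs to another method**, the mean of answered items. That is fair as a point about carrying the limit over alone, so the fix takes the method and the limit together.
- **Part of the plan cannot be seen.** SAP 8.4.6, on exploratory endpoints, is listed in the contents but its text is not visible in this copy. A restriction there cannot be ruled out.

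**Conclusion.** The concern holds in limited form. As written, the MNSI rule has no cap and no visit restriction, unlike the rule for the other scales in the same section, and it acts on a change score.

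At baseline it can add up to 1 point of false improvement per missing history item. A reader might infer that improvement is guaranteed, or that the drug is favoured. Neither follows: the effect is zero when the true answer already scores, and it balances between arms in expectation.

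At follow-up, largely blank history forms score near 13, and wholly missing ones score 13 if the rule is read to include them. The arm contrast is biased only if missingness or the size of the jump differs by arm. The illustrative 0.25 to 0.45 points rests entirely on assumed inputs: mean scores of 4 to 8, a 5-percentage-point imbalance, and the whole-form reading.

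The consequence is confined to an exploratory endpoint outside the testing hierarchy of SAP 7.4. The primary and key secondary conclusions are untouched. This is a minor point, worth correcting because it is cheap and settles a choice before unblinding.

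**What to change.** Amend the MNSI paragraph of SAP 7.6.2 before unblinding:

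1. Use one rule at all visits, the one the section already applies to the other scales. Prorate from the answered items in the domain when fewer than 25% are missing (at most 3 of the 13 scored history items). Otherwise set the domain total to missing.
2. State that a wholly missing form is not imputed.
3. Keep worst-case scoring of post-baseline items as a sensitivity analysis only. It should not be the main rule beside a prorated baseline, because an item missing at both visits would then tend to show false worsening.
4. Reword the opening sentence to say that item data stay as observed and that imputation is used only to form the domain total.
5. Check that SAP 8.4.6 agrees.

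The cost is SAP wording and a small programming change, with no new data and no effect on the design or the primary analysis. The downside is that a few participants drop out of the MNSI change summary, and their number should be reported by arm and visit.
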